SARS-CoV-2 is a coronavirus that emerged in China in late 2019 causing a novel Corona-Virus Induced Disease (COVID-19). COVID-19 is spreading rapidly throughout the world. While a proportion of people with COVID-19 have sufficiently severe symptoms to require hospitalization at the time of initial symptom onset, in others the disease may remain mild, and in some cases there has been observed a worsening of symptoms a few days after initial presentation with relatively mild symptoms. There is an urgent need for understanding the progression of disease for individuals with SARS-CoV-2 infection/COVID-19 who do not require immediate hospitalization.

This is an international, observational cohort study of adults with SARS-CoV-2 infection/COVID-19 managed as outpatients (not hospitalised). This study will also be a platform for the enrolment of outpatients for randomized trials that will be conducted by the INSIGHT group.

Those with confirmed SARS-CoV-2 infection will form an observational cohort study and be followed for 28 days. Procedures and data collection have been streamlined to facilitate the enrolment of a large number of adults at INSIGHT sites around the world.

The general aim of this study is to estimate the rate of disease progression for adults testing positive for SARS-CoV-2. The primary endpoint for this study and the basis for sample size is hospitalization or death during the 28 day follow-up period. In some locations special facilities are being built/utilized for quarantine/public health reasons for those who are SARS-CoV-2 positive. Hospitalization is defined as a stay for at least 18 hours, irrespective of reason, at a hospital or one of these special facilities after study enrolment.

Secondary outcomes include participant-reported health status and change in severity of dyspnoea.

As the understanding of the natural history of COVID-19 improves based on this and other studies, inclusion criteria and the data collection plan, including the outcomes assessed in this protocol, may be modified.

Study Objectives

The two primary objectives of this observational study are:

Among participants testing positive for SARS-CoV-2:

1. Estimate the rate of hospitalization or death during the 28 day follow-up period.
2. Identify risk factors for hospitalization or death.

Other objectives are:

1. Compare characteristics, including demographics, co-morbid conditions or immunosuppression, and other risk factors for disease progression, including hospitalization or death, for the global cohort and by geographic region between those who have a positive test for the SARS-CoV-2 virus versus those who have a negative test.
2. Among those positive for SARS-CoV-2:
 - a. Evaluate health status and the percentage reporting excellent or very good health status during follow-up.
 - b. Determine the percentage reporting a return to pre-morbid health status during follow-up.
 - c. Evaluate change in severity of dyspnoea using a standardized questionnaire during follow-up.
3. In a substudy involving selected sites, establish a repository of baseline upper respiratory and blood samples for future studies. These studies will be aimed at molecular characterization of SARS-CoV-2, and the measurement of biomarkers that predict progression of disease. Among participants co-enrolling in INSIGHT 004: Genomics, DNA will be extracted for studies of host genetics to investigate the pathophysiology and host-viral interactions of COVID-19.
4. Use the data collected to inform the design of future randomized intervention studies aimed at reducing the rate of disease progression and morbidity.

Participant Selection

To be eligible for enrolment participants must be ≥ 18 years of age, not be hospitalized (outpatients), and have a signed informed consent. Participants with SARS-CoV-2 infection will be followed for 28 days from enrolment.

Study Plan

Participants who consent for the study and have SARS-CoV-2 infection/COVID-19, will be followed for 28 days in an observational cohort study.

Procedures and data collection have been streamlined to facilitate the enrolment of a large number of adults at INSIGHT sites around the world.

The general aim of this study is to identify risk factors for disease progression, e.g., hospitalization or death. This information will be used to plan and rapidly enrol randomized trials of treatments for COVID-19. Protocols which are developed for the randomized trials by INSIGHT will be separate from this protocol.

2 Background and Rationale

In December 2019, the Wuhan Municipal Health Committee identified an outbreak of viral pneumonia cases of unknown cause. A novel coronavirus was rapidly identified by sequencing and named severe acute respiratory syndrome coronavirus 2 (SARS-CoV-2), and the illness caused by infection with SARS-CoV-2 has been named Corona Virus Induced Disease 2019 (COVID-19). By February 2020 sustained community transmission outside China was apparent, and as of March 27 there are more than 500,000 cases reported in over 100 countries, with over 25,000 deaths. The World Health Organization declared the outbreak a Public Health Emergency of International Concern on 30 January 2020 and subsequently stated that the outbreak could be characterized as a pandemic on March 11, 2020.^{1,2}

Over the course of the past several weeks there have been several reports describing the clinical manifestations of SARS-CoV-2 infection and factors associated with greater disease severity, mainly in hospitalized patients.³⁻¹⁶ While COVID-19 may have a lower fatality rate than previous coronaviruses like MERS and SARS-CoV-1, it is more contagious.⁵ Current estimates of the fatality rate range from 0.5 to 3.5% overall (versus 0.1% for seasonal influenza), and are likely higher in key risk groups including the immunocompromised.

Reports to date have focussed largely on hospitalized patients and included descriptive information on the patients as well as estimates of associations between those characteristics and disease severity. Older age has been found to be strongly related to greater severity and poorer outcome,^{7,12,17} as have the presence of conditions such as hypertension, diabetes and coronary heart disease.^{5,7,14} Patients with underlying cardiovascular disease who have elevated troponin T levels are at increased risk of death compared to those without elevated troponin T levels.¹⁸ Other risk factors identified include cigarette smoking^{7,12,19} and raised BMI.^{10,16} Gender has not shown a consistent relationship with disease severity.^{4,7} Specific symptoms at presentation that have notably been associated with greater likelihood of progression to more severe disease include shortness of breath and elevated body temperature.^{7,9}

Data on the relationship between the use of routine medications for chronic conditions and COVID-19 outcomes are limited. It has been hypothesized that since the tissue receptor for SARS-CoV-2 is angiotensin-converting enzyme 2 (ACE2), and higher levels of ACE2 can protect against acute respiratory distress syndrome (ARDS), that the angiotensin receptor blockers and statins upregulate ACE2 and that these might be used to treat COVID-19.²⁰ On the other hand, it has also been suggested that treatment with ACE2-stimulating drugs in people with diabetes and hypertension could increase the risk of developing severe and fatal COVID-19.²¹ One small study has found no association between use of an angiotensin-converting enzyme inhibitor or angiotensin II receptor blocker and risk of death in COVID-19.¹⁰

There is currently little data available in people with COVID-19 who are managed as outpatients. It would be useful to identify risk factors associated with progression of COVID-19 in non-hospitalized individuals leading them to require hospitalization and/or

treatment for COVID-19. This will provide critical information for clinical service planning, and further inform the development of novel therapeutics.

INSIGHT is currently enrolling hospitalized patients with COVID-19 in the INSIGHT FLU 003 Plus observational study. This observational study of outpatients with COVID-19 will complement FLU 003 Plus and address gaps in our knowledge about risk factors for disease progression that lead to hospitalization or death.

Recognizing the critical importance of maintaining front-line clinical services in responding to COVID-19 and protecting health care workers, this study is designed with minimal data collection requirements with careful attention to management of the risks of service diversion and onward disease transmission. To that end, we considered the literature reviewed above and developed a streamlined data collection plan for collection of baseline and follow-up data for adults who test positive for SARS-CoV-2. Throughout this document when referring to testing for SARS-CoV-2, this refers to a test that directly detects SARS-CoV-2 i.e. a nucleic acid test that detect the presence of viral RNA, typically a PCR test, or a viral antigen test, not an antibody test.

The data from this cohort study will be regularly summarized and may be modified based on interim results or the findings from other studies. Plans are underway for potential extension of follow-up through 5 years for the purpose of assessing long-term complications and durability of antibody response. These plans will be developed under a separate protocol or an extension to this protocol, with existing participants invited to participate.

3 Methodology

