3.3 Endpoints

The primary endpoint is hospitalization or death during the 28 day follow-up period. Special facilities are being built for the care of COVID-19 patients requiring medical care. Hospitalization is defined as a stay for at least 18 hours, irrespective of reason, at a hospital or one of these special facilities after study enrolment.

Key secondary outcomes include:

- Participant-reported evaluation of health status
- Change in severity of dyspnoea.

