3.4 Sample Size

Sample size is open-ended for this observational study. We estimate that several hundred sites will participate and will enrol approximately 10,000 adults with SARS-CoV-2 infection. Sites in diverse geographic locations on several continents will participate.

For participants with COVID-19, statistical considerations are summarized below. Information on rates of a composite outcome of hospitalization or death for the target

population is scarce, and rates are expected to vary across geographic locations, and possibly over time. Therefore, initial analyses will be descriptive, and sample size estimates will be updated based on the observed event rates, prevalence of risk factors, and newly emerging research questions.

For power calculations, we conservatively assume that 500 out of 10,000 (5%) participants will experience the composite outcome of hospitalization or death by day 28. This is based on the expectation that persons with mild symptoms will be discouraged from seeking SARS-CoV-2 testing at the height of the pandemic, while persons presenting with severe symptoms would not be eligible for this protocol.

Table 1 below summarizes the sizes of the associations of risk factors (dichotomized) with hospitalization or death (odds ratios) that can be detected with 80% and 90% power, using 2-sided tests with significance level of 0.05, assuming 500 or 100 events. For example, with 500 events, an odds ratio of 1.51 can be detected with 80% power for a risk factor with 10% prevalence. For analyses within subgroups, e.g., by age, event numbers may be smaller. With 100 events, an odds ratio of 2.32 can be detected with 80% power for a risk factor with 10% prevalence.

Prevalence of Risk Factor	500 events		100 events	
	80% Power	90% Power	80% Power	90% Power
5%	1.73	1.85	2.99	3.31
10%	1.51	1.59	2.32	2.55
25%	1.34	1.40	1.86	2.02
50%	1.30	1.35	1.76	1.93

Table 1. Odds ratios that can be detected with 80% and 90% power, assuming 500 or 100 persons are hospitalized or die.

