3.5.1 Inclusion Criteria

- ≥ 18 years of age
- Not hospitalized
- Signed informed consent.

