3.6 Study Plan

The study plan is depicted in Figure 1.

Figure 1: Study plan for participants undergoing SARS-CoV-2 testing and consenting to participation in this observational study.

Footnote

*on the day of enrolment or test done within 3 days before enrolment

¥ includes COVID-19 related out-patient treatments

Enrolment

Outpatient testing for SARS-CoV-2 may be performed in a variety of ways and for a variety of reasons. To avoid risk to health care workers, in many locations, special facilities are being identified for rapid identification of those with COVID-19. We refer to these as “testing stations”. Since the testing stations are likely to be overwhelmed with people seeking testing, we anticipate that separate areas will have to be identified to consent participants for this research study and to collect the required data. We refer to these as “research stations”. Collaborations between the testing and research stations will be important.

For participants who consent to the study, permission to release medical records will be sought and reasons for hospitalization and events during hospitalization will be requested. Information regarding demographics; medical history, including co-morbidities; onset date of symptoms; targeted symptoms, including difficulty breathing; smoking; and targeted medications will be obtained. Contact information for one or two persons who know(s) the participant’s whereabouts will also be recorded.

At the time of enrolment, selected sites participating in a substudy (see Appendix F) will be asked to obtain separate consent for the swabs from the upper respiratory tract and a blood sample sufficient for 4mL of serum to be shipped to a central repository for future respiratory virus research; and 2) co-enrolment in the INSIGHT Genomics Study (INSIGHT 004) where a blood sample sufficient for obtaining 6mL whole blood will be collected and stored. These specimens will be sent to a central repository in the United States for storage.

Proposed research utilizing stored specimens collected per this protocol will be reviewed and approved by the Protocol Team, the INSIGHT Scientific Steering Committee, and NIAID.

Disclosure of SARS-CoV-2 Test Result

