4.1 Data Analysis

Simple descriptive statistics will be used to describe all participants enrolled, as well as those with and without a positive test for SARS-CoV-2. Participant characteristics at enrolment will be summarized by geographic region, and by calendar time within geographic region. Participant characteristics will be compared for those with and without a positive test for SARS-CoV-2.

Symptoms, including severity of dyspnoea, will be summarized, and determinates of a positive test will be identified using logistic regression models. Factors other than symptoms include, for example, age, sex, co-morbidities, and time since onset of symptoms.

For participants who tested positive for SARS-CoV-2, follow-up data will be collected at days 7, 14, and 28. Disease severity at each time point will be summarized in an ordinal outcome that considers death, hospitalization, and general health status.

Risk factors for the outcomes (e.g., hospitalization, worsening of general health status) at 7, 14, and 28 days after enrolment will be examined using logistic regression models. Reasons for hospitalization will also be considered and analyses for specific reasons for hospitalization will be pursued. Risk factors will include demographic factors (e.g., age, sex, geographical region), clinical factors (e.g., co-morbidities, smoking status), symptoms and severity of dyspnoea at enrolment, and calendar time (to assess the influence of season, or a change in disease severity in the study population over time).

In addition to describing disease status at fixed time points, Kaplan-Meier estimates will be used to describe time to the composite outcome of hospitalization or death, overall and within subgroups. Factors associated with time to hospitalization or death will be investigated using Cox proportional hazards models.

All statistical models will be stratified by geographic region, unless the event numbers are too low. We will consider other stratifying models that include stratification by geographic region and calendar time if event numbers are sufficient.

As new data on COVID-19 become available, from this and other studies, data collection and analysis may change to address emerging research questions. Further details on the proposed data analysis will be provided in a Statistical Analysis Plan.

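### The primary endpoint has two meanings: the synopsis counts stays in quarantine facilities, while section 3.3 describes facilities for medical care

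*Protocol*

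**What the plan says.** The synopsis and section 3.3 of the protocol share one operative sentence: "Hospitalization is defined as a stay for at least 18 hours, irrespective of reason, at a hospital or one of these special facilities", counted after enrolment. Which facilities are meant depends on the sentence just before it, and that sentence differs.

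- Synopsis: "In some locations special facilities are being built/utilized for quarantine/public health reasons for those who are SARS-CoV-2 positive".
- Section 3.3 (Endpoints): "Special facilities are being built for the care of COVID-19 patients requiring medical care".

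The purpose of the endpoint appears in the synopsis, under Study Plan: "The general aim of this study is to identify risk factors for disease progression, e.g., hospitalization or death". The synopsis also gives estimating the rate of disease progression as the general aim. Section 3.4 plans for the event count as follows: "we conservatively assume that 500 out of 10,000 (5%) participants will experience the composite outcome of hospitalization or death by day 28". It supports the 5% with expectations about who seeks testing and how severe their symptoms are. Isolation stays are not mentioned.

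Two other provisions bear on the point. Section 3.6 says that "reasons for hospitalization and events during hospitalization will be requested". Section 4.1 plans further analyses for specific reasons for hospitalization and states: "All statistical models will be stratified by geographic region, unless the event numbers are too low".

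**The concern.** Both primary objectives, the 28-day rate and its risk factors, rest on this one event. If the facilities include quarantine sites, a positive test plus a local isolation policy is enough to produce an event, and every member of the followed cohort is positive. Such a stay says nothing about whether the disease progressed.

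Three things are at stake.

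- The 28-day rate is inflated, and the protocol intends these data to inform the design of later randomized trials.
- Odds ratios are pulled toward 1 if placement is unrelated to the risk factor. If it is related, they are pulled toward whatever determines placement.
- A site working from the synopsis and a site working from section 3.3 could classify the same stay differently.

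Counting hospital stays for any reason is a legitimate choice and is not criticised here. The defect is that the any-reason rule extends to facilities whose purpose the protocol states in two ways.

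**Working it through.** **1. The two definitions applied to one case.** Take a participant without worsening symptoms who is sent to an isolation facility for two days.

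| Source | What the facilities are for | Is this stay a primary event? |
|---|---|---|
| Synopsis | quarantine or public health | yes |
| Section 3.3 | care of patients who need medical care | no, if the facility only isolates |

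No other section says which description governs.

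**2. The plan's own figure (section 3.4).** 500/10,000 = 5%. The worked example is an odds ratio of 1.51 at 10% prevalence, two-sided 0.05, 80% power. With 1,000 exposed, 9,000 unexposed and 5% risk in the unexposed, the exposed risk is 0.0736. The unpooled standard error is √(0.0736×0.9264/1000 + 0.05×0.95/9000) = 0.00857, so z = 0.0236/0.00857 − 1.96 = 0.80 and power is 78.7%. A pooled test with 5% overall gives 84.1%. The stated 80% lies between the two, so the example is a sound starting point. The power figures in step 5 use the pooled test.

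**3. Quarantine-only stays added to 5% true progression.** Assumptions: N = 10,000, prevalence 10%, true OR 1.51, placement unrelated to the risk factor. Solving 0.9p₀ + 0.1p₁ = 0.05 with OR 1.51 gives p₀ = 0.04774 and p₁ = 0.07037. If a fraction i of non-progressors is isolated, each risk becomes p + i(1 − p).

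For i = 0.05, the unexposed risk is 0.04774 + 0.05×0.95226 = 0.09535 and the exposed risk is 0.07037 + 0.05×0.92963 = 0.11685. The overall rate is 0.05 + 0.05×0.95 = 9.75%, and the OR is (0.11685/0.88315)/(0.09535/0.90465) = 1.26.

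| i | Observed rate | Unstratified OR |
|---|---|---|
| 1% | 5.95% | 1.43 |
| 5% | 9.75% | 1.26 |
| 10% | 14.5% | 1.17 |

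**4. Does stratification by region repair it?** In the best case, strata match isolation practice exactly. A share s of the cohort lives where a fraction q of non-progressors is placed, and nobody is placed elsewhere. The stratified OR is the Mantel-Haenszel value on expected counts.

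| q | s | Rate | Unstratified OR | Stratified OR |
|---|---|---|---|---|
| 50% | 5% | 7.4% | 1.34 | 1.41 |
| 50% | 10% | 9.75% | 1.26 | 1.33 |
| 50% | 20% | 14.5% | 1.17 | 1.24 |
| 5% | 5% | 5.2% | 1.49 | 1.49 |
| 5% | 10% | 5.5% | 1.46 | 1.47 |
| 5% | 20% | 6.0% | 1.43 | 1.43 |

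Stratification recovers part of the odds ratio and none of the overall rate. Within an isolating location, isolation stays make up q×0.95/(0.05 + q×0.95) of events: 49% at q = 5% and 90% at q = 50%.

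**5. The other reading: 5% is already the composite as defined.** Let a fraction f of the 500 events be quarantine-only. Progression is then 5%×(1 − f), and i = (0.05 − progression)/(1 − progression). For f = 25%, progression is 3.75% (375 events) and i = 0.0125/0.9625 = 0.0130. The group risks move from 0.0358 and 0.0530 to 0.0483 and 0.0653, so the observed OR is 1.38.

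| f | Progression rate | Observed OR | Power, all 500 events | Power, quarantine-only stays excluded |
|---|---|---|---|---|
| 10% | 4.5% | 1.46 | 77% | 81% |
| 25% | 3.75% | 1.38 | 64% | 75% |
| 50% | 2.5% | 1.25 | 36% | 60% |

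With placement unrelated to risk, removing these events does not cost power at fixed N, although fewer events remain.

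**The case against.** The strongest reply is that the operative sentence is the same in both places and only the lead-in differs. The synopsis names quarantine facilities and at once counts stays there for any reason, so the breadth may be deliberate: a count that ignores reasons needs no adjudication, which suits a streamlined study at several hundred sites. The primary objectives are worded as hospitalization or death; progression is named only in the general aims. Reasons for hospitalization, symptoms and health status are collected, so isolated but well participants can be identified later. The 5% is provisional, since section 3.4 expects to update it. At low isolation frequencies the effect is minor.

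Much of this limits the size of the problem without removing it.

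- Deliberate breadth is possible, but the protocol does not state it, and section 3.3, the formal endpoint section, does not carry it. The two passages need reconciling on either reading.
- The by-reason analyses are additional, and the stratification is conditional on event numbers. Neither changes what counts as a primary event.
- That sites would actually code differently is a risk, not an established fact, because the case report forms are not in the protocol.
- The missing allowance in the 5% is a consequence of the ambiguity, not a separate error.
- It is fair that the 75% power assumes every quarantine-only reason is known. If 25% or 50% of those stays lack a reason and remain events, power is about 72% or 69%, still above 64%.
- It is also fair that a reason-based rule adds some site judgement.

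**Conclusion.** The concern holds. The primary endpoint is wrong as written: one definition sentence points to two different kinds of facility, and under the synopsis an isolation stay of 18 hours in a well person counts as disease progression. This follows from the text and depends on no assumption.

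The size does depend on assumptions, because the protocol gives no frequency of isolation stays. Over an illustrative 1% to 10% of non-progressors isolated independently of risk, the rate moves from 5% to between 5.95% and 14.5%, and an odds ratio of 1.51 to between 1.43 and 1.17 without stratification. At the low end (5% placed, in locations holding 5% of the cohort) the change is slight: a rate of 5.2% and an odds ratio of 1.49. If placement is related to a risk factor, the direction of bias in the odds ratio cannot be fixed in advance.

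The point should be fixed, since it touches both primary objectives and the repair is cheap.

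**What to change.** Use one definition in the synopsis and section 3.3. The primary event would be death, a hospital stay of at least 18 hours for any reason, or a special-facility stay of at least 18 hours that is not solely for quarantine or isolation. In addition:

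- count special-facility stays with missing or mixed reasons as events by default;
- report quarantine-only stays as a separate outcome;
- keep the present all-stays definition as a sensitivity analysis;
- while editing, state whether someone already in such a facility satisfies "Not hospitalized" in section 3.5.1. This is a clarification and not part of the case above.

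The cost is the endpoint wording and a yes/no quarantine-only item for special-facility stays. Section 3.6 already asks for reasons for hospitalization, but the Appendix B schedule lists only vital and hospitalization status at follow-up. The default rule leaves some quarantine stays in the endpoint, isolation-only stays in an ordinary hospital still count, and the number of primary events may fall.
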